2.1 Objectives & Hypotheses	
Hypothesis: The development of alternative methods of screening for HCV infection in persons who inject drugs (PWID), as part of a harm reduction strategy at “Cañada Real” shantytown (Madrid), may facilitate diagnosis of the disease in this population, increase the frequency of referral to hospital and administration of appropriate HCV treatment and thus reduce the prevalence of HCV.
 
Objectives: The overall objective of this project is to evaluate whether the implementation of an alternative method of HCV screening in PWID from "Cañada Real " (Madrid) can improve the localization of HCV-infected patients for subsequent referral to the Hospital, administration of HCV antiviral therapy and cure of hepatitis C. The effectiveness of the intervention in each of the phases of the project will be assessed.
 
Main objectives:
 
 1. To develop and validate an alternative method of screening for active hepatitis C virus (HCV) infection based on collection of capillary blood via finger pricking and Whatman™ cards (dried blood). 2. Implementation of a screening program in PWID from "Cañada Real" (Madrid) aimed at early HCV detection (diagnostic) and early HCV treatment as part of a harm reduction strategy, and 3. To assess the effectiveness of our alternative HCV screening test in PWID through evaluation of the impact on the patients' health (referrals to health centers, number of treated patients, and the percentage of cure). 
Secondary objectives:
 
 4. Estimation of the prevalence of HVC active infection or HCV resolved spontaneously with the methodology developed. 5. To estimate the prevalence of other chronic viral infections (eg, HIV, HBV, and HDV) that are relatively common in PWID. 6. To estimate the prevalence of active HCV infection 24 months after the first intervention in “Cañada Real”. 7. To assess factors associated with HCV infection and transmission through an epidemiological survey, which will collect demographic data and risk behaviors.

**2.2
Background &
Rationale,
Significance of
Selected
Topic &
Preliminary
Data**

HCV infection is a major health problem worldwide. The main source of infection is currently parenteral drug use, especially in more developed countries. HCV infection is the main cause of liver-related death and the principal indication for liver transplant in industrialized countries. Increased knowledge of the molecular mechanisms involved in the cell cycle of HCV has made it possible to develop a new family of drugs known as direct-acting antivirals (DAAs). Treatment courses are now short and very safe. In addition, dosing is convenient and efficacy and cure rates are high.

Spain has one of the highest HCV infection prevalence values in Europe. The estimated prevalence of HCV antibodies is 1.7%, and the prevalence of positive viral load in adults is 1.2%, that is, 472,000 adults with active infection. However, it is estimated that only 40% of HCV-infected persons in Spain have actually been diagnosed, probably because conventional screening strategies have not been widely applied and have proven to be of limited efficiency both in the general population and in hard-to-access risk groups. Despite the extent of this health problem, the true prevalence of HCV infection in our area is not known. The recently established National Hepatitis C Plan opened a line of investigation aimed at quantifying the problem, describing the epidemiological characteristics of those infected, and establishing preventive measures. The National Hepatitis C Plan, which came into force on April 1, 2015, has been a definite boost in the treatment of hepatitis C in Spain. In the first year of the Plan, more than 40,000 patients with HCV have been treated, acquiring similar cure rates to those reported in clinical trials. HCV therapy in Spain is widely available and PWID are considered to be a priority population.

Screening for HCV infection is cost-effective, since early identification helps limit the transmission of the virus and enables patients to benefit from drug therapy and non-pharmacological measures that prevent them from developing advanced forms. In this context, early diagnosis of infection is becoming increasingly important, as is the use of DAAs, which represent the first step on the road to eradicating HCV infection. Screening for HCV infection is currently based on serological testing followed by further extraction to confirm active infection based on the HCV-RNA load in blood. Several international organizations have stressed the need to find new ways of reaching out to patients in the form of alternative tests for detecting active infection (presence of HCV-RNA in blood) in order to enhance screening for HCV infection, diagnosis, referrals to health centers, and treatment.

Intravenous injection continues to be the most frequent route of transmission of HCV in Europe (79% of new infections in 2012) and is the key driving force in the perpetuation of the epidemic. The percentage of undiagnosed PWID is probably greater than in the general population, given that this vulnerable group has little access to the health system. Accordingly, the World Health Organization (WHO) stresses that all HCV-infected persons should have equal access to prevention, diagnosis, and treatment and that special efforts must be made with regard to more inaccessible population groups.

Modeling studies indicate that the only way the prevalence of HCV infection can be substantially reduced is through the early publication of across-the-board public health strategies that include significant increases in the frequency of diagnosis and access to treatment³.

PWID are at high risk from blood-borne infections, including human immunodeficiency virus (HIV) and HCV through the sharing of needles and injection equipment. Harm reduction refers to policies, programs and practices that aim to reduce the harms associated with the use of drugs in people unable or unwilling to stop. Harm reduction began to be discussed frequently after the threat of HIV spreading among and from PWID was first recognized. However, similar approaches have long been used in many other contexts for a wide range of drugs. There is persuasive evidence from the literature that harm reduction approaches greatly reduce morbidity and mortality associated with drug use and combined prevention measures (Needle and syringe programmes & opioid substitution therapy) contribute to the reduction of the spread of

HIV and HCV infections. Although there is concern that HCV re-infection may negate the potential benefits of treatment, the reported rates of reinfection following successful HCV treatment among PWID are low, especially when combining high coverage of harm reduction measures.

Cañada Real is a major shantytown on the outskirts of the city of Madrid. It is estimated that 90% of the illegal drugs in the Madrid region are sold and consumed in Sector VI of Cañada Real and that between 4000 and 6000 people per day go to this shantytown for their drug doses. The Anti-Drug Agency (Agencia Antidroga) runs a daily mobile unit in the area as a harm reduction strategy. The remit of the unit is to minimize damage from drug consumption by taking health-related, psychological, and social measures. It deals mainly with outreach drug consumers (individuals who are outside the reach of the health system and have great difficulty accessing it). This harm reduction unit identifies drug users at risk, offering them needles, syringes, opioid substitution therapy and screening for HIV and HCV. When a PWID tests positive for HIV or HCV, he is referred to Infanta Leonor Hospital for appropriate therapy. The harm reduction team accompanies the drug user to hospital and ensures his follow-up and adherence to therapy. Recent hepatitis C test and care programs have identified the use of patient navigators or care coordinators to be an important intervention in overcoming challenges to linkage to and retention in care

In Spain, prevention and screening of HCV infection is ensured mainly through primary health care. Infection is diagnosed using serological tests followed by retests to confirm active infection. The tests are used to detect HCV RNA in blood and are carried out at specialist health centers. However, a large number of people at high risk of infection do not visit health centers regularly, and even when they do, the centers lose track of a very high percentage of patients in the follow-up stage. Thus, a simple screening method or an alternative diagnostic test that can be used in situ could make testing more widely accepted and improve rates of diagnosis, referral, and treatment.

There are several quick, highly specific, highly sensitive tests on the market for detecting HCV antibodies. The tests are fast, simple, and provide results on site. However, the need for further testing to confirm results usually involves a number of visits for testing and collection of results. Consequently, many patients are lost during follow-up. Screening strategies should therefore be capable of ensuring that active infection is correctly diagnosed. Changes in the screening algorithm have recently been proposed so that HCV-RNA can be detected directly, especially in relatively inaccessible high-risk populations such as PWID.

Here, we seek to validate and implement an alternative method to screen for HCV and other viruses in an attempt to facilitate diagnosis of HCV infection, increase referrals to specialist health centers, and thus increase treatment coverage in our area. The alternative screening method proposed requires five drops of capillary blood to be collected by finger pricking onto Whatman cards. This method is more widely accepted than venous extraction and has enabled diagnosis rates to be improved by two- to six-fold among PWID at community services in the United Kingdom.

Several studies have shown the validity of dried blood samples for detecting HCV RNA using amplification techniques. Moreover, dried blood samples can also be used to perform HCV genotyping and phylogenetic studies, which can reveal transmission networks. However, although using dried blood samples offers advantages in terms of diagnosing active infection, it does not preclude the need to call individuals back in order to give them the results and provide them with suitable advice, as samples are sent to the laboratory and the results may take some time to come through.

Screening via finger pricking using Whatman cards is simple and cheap and can be applied with only minimal training. It obviates the need for venipuncture and syringes, requires only minimal amounts of blood, and takes up little storage space. Consequently, samples are easy to carry and handle. Proactive screening and active approaches to users will enable us to quantify the problem, learn the epidemiological

	
characteristics of HCV-infected patients, and thus establish more suitable preventive measures and a circuit of referral to specialist centers for confirmation of diagnosis and treatment.
 
Screening, diagnosis and treatment of HCV in PWID, should be part of a harm reduction strategy. Treatment of HCV infected PWID should be delivered in a multidisciplinary care setting with services to reduce the risk of reinfection and for management of the common social and psychiatric comorbidities in this population. More frequent diagnosis, new methods that prevent loss of tracking, and access to antiviral treatment are all strategies that must be implemented jointly if the prevalence of HCV infection in our setting is to be reduced.

2.3 Study Design	
TYPE OF STUDY: Multi-center: "Infanta Leonor" Teaching Hospital (HUIL), National Microbiology Center–Carlos III Health Institute (CNM-ISCIII), and the Harm Reduction Unit (HRU) (Madrid Positivo and the Anti-Drug Agency).
 
DURATION OF THE STUDY: 24 months.
 
DESIGN OF THE STUDY: Cross-sectional.
 
SCOPE OF THE STUDY: The study population comprises persons who visit the Cañada Real Galiana shantytown on the outskirts of Madrid, where 90% of illegal drugs in the region are sold and consumed. It is estimated that between 4000 and 6000 people per day visit the shantytown for their dose. The regional government's Anti-Drug Agency has a mobile HRU operating daily in the area. The unit provides screening tests to anyone who is willing to take them, regardless of whether they are already aware of their serological status or not. Screening includes education on prevention of HCV infection and other transmissible diseases.
 
PHASES OF THE STUDY
 
1) PHASE I: Setting and calibration of the laboratory techniques needed to carry out the study. The screening method will be validated with dried blood spots from Whatman 903™ cards taken from volunteer patients at HUIL. The results will be compared with the results of a venous blood sample taken from the same individual at HUIL. The sensitivity (Se), specificity (Sp), positive predictive value (PPV), and negative predictive value (NPV) of the diagnostic tests will be determined.
 
2) PHASE II: Screening for HCV and other viruses (HIV, HBV, HDV) using dried blood samples on Whatman™ cards in subjects from Cañada Real based on the results of the laboratory tests performed in phase I. The data and samples will be collected by the HRU. All the samples collected will be sent by courier to the CNM-ISCIII for processing and analysis.
 
3) PHASE III: Evaluation of the effectiveness of the intervention. Subjects who had a positive result in the screening performed in Cañada Real Galiana will be contacted and offered the possibility of referral to HUIL, where they will have access to standard confirmation tests. Here, test accuracy will be evaluated at population level. Patients will have access to HCV treatment and will be followed for assessment of the impact of the program on patients' health (referrals to health centers, percentage of treated patients, and the percentage of virological response). As part of the harm reduction program patients will be screened periodically after therapy to detect HCV reinfection.
 
COLLECTION AND PROCESSING OF SAMPLES
 
Biological samples will be collected according to the study protocol as dried blood spots on Whatman 903 cards (50-75 µl of blood). The blood samples obtained will be processed according to the protocol for handling samples set out in Annex 1 of the


protocol.

The Whatman 903 cards used to collect whole blood will be handled by healthcare professionals. The device consists of a small card with five circles for collecting one drop of blood each. The card is attached to a record card where demographic information on the individual being tested is recorded. A small amount of capillary blood from the user's ring or middle finger is collected on the sample collection area and then allowed to dry at room temperature for three hours. The card is then made ready for transportation to the screening laboratory. It must be taken to the laboratory within 15 days of collection.

Samples will be sent to the CNM-ISCIH for laboratory testing. The cards will be stored at -80°C .

PHASE I: INTERNAL VALIDATION AND REFINING OF THE TECHNIQUE

Once the ethics committee has approved the study, samples will be obtained by finger pricking using Whatman 903TM cards at visits to the Internal Medicine department of HUIL. All patients visiting the department, for whom recent analytical data (serology results for HCV, HIV, HBV, and HDV, as well as HCV-RNA viral load and HCV genotyping collected during the previous 15 days) will be asked to take part in the internal validation study. Patients whose analyses were performed elsewhere or are not recent will not be included. Healthy individuals, i.e. those who have tested negative for HCV, HIV, HBV, and HDV will also be included. Individuals will be included in the validation consecutively until the preset number is reached (see below).

A total of 100 patients and 50 healthy individuals will be included to validate the screening test. Successive samples will be taken, and patients with genotypes 1a, 1b, 2, 3, and 4 will be included. National data indicate that the distribution of the most frequent genotypes in Spain is as follows: 1b, 44%; 1a, 26%; and 3, 20%. Therefore, these will be the genotypes most widely represented in our study. The 50 healthy individuals (negative for HIV, HBV, HCV, and HDV) will be obtained from the family members accompanying patients on medical visits, who will be invited to take part in the study. One dried blood sample will be taken by finger pricking and another simultaneous sample will be taken by venipuncture. The venipuncture sample will be processed through the usual channels at the center.

Participants will be given an information leaflet and a specific informed consent form. Samples will be processed according to the study protocol (Annex 1). Clinical and epidemiological data will be recorded in a database that can be accessed by researchers from the HUIL and the CNM-ISCIH. The variables shown in section 2.4 will be recorded. This file has been included in the Register of Data Files of the ISCIH.

ELISA: A disc with a sample of dried blood will be placed in a microtube containing 300 μl of 0.5% buffer solution (PBS/BSA) and processed at $4-8^{\circ}\text{C}$ for 18-24 hours. After incubation, elutes from the dried blood samples will be tested for the presence of antibodies against HCV, HIV, and HDV, as well as for HBV surface antigen (HBsAg). Negative samples will not undergo further testing and will be considered non-infected. Positive samples will be tested using real-time PCR to confirm the positive results.

Real-time PCR: Nucleic acids will be extracted using the DSP virus pathogen kit (QIAGEN, Hilden, Germany). The samples will be stored at -80°C until use. A specific HCV test will be performed to confirm active HCV infection (HCV-RNA positive) on a Rotor Gene Q unit (QIAGEN).

PHASE II: SCREENING AT CAÑADA REAL GALIANA

Screening for HCV and the other viruses (HIV, HBV, and HDV) covered by this project will take place at Cañada Real Galiana. Screening will be conducted by nursing personnel hired specifically for that purpose. An active search will be made for

individuals who come into the shantytown from outside, and the detection test will be offered to everyone regardless of whether or not their serological condition is already known. Selection of individuals for screening will be random and consecutive.

Nursing personnel will generally be accompanied by an educator from the HRU. PWID will be offered information on prevention and the importance of early diagnosis and referral to health centers.

Information will then be provided on the goals of the study, and persons who agree to take part will be required to sign an informed consent form, provide contact data for subsequent location, and provide basic social and demographic data and information on their consumption habits. Regardless of whether or not individuals agree to take part in the study, they will all be given a card containing basic information on prevention and contact data for the internal medicine department of HUIL and the HRU.

Data will be recorded on social and demographic details, the consumption habits of each PWID, and the acceptability of the screening test. All data will be recoded in the database by the nurse or the educator using a mobile device with Internet capability and REDCap software. Informed consent forms will be kept in the files of the researcher at the HRU office.

The Whatman™ cards will be stored in a portable refrigerator after processing (see below) and shipped via courier to the National Microbiology Center (CNM) for analysis.

If a test result is positive, the patient will be contacted and offered referral to a specialist health care center in accordance with the study algorithm to confirm the result and assess whether monitoring should begin. All subjects included in the study may contact the medical department or the Harm Reduction Unit directly to make an appointment and collect the results of their tests.

PHASE III: EFFECTIVENESS OF THE INTERVENTION

Evaluation of the effectiveness of the intervention. Drug users who test positive will be contacted and offered the possibility of referral to a specialist health care center, where access to standard confirmation tests used in hospital and access to treatment will be offered. As specified in the consent form, if a patient with a positive result cannot be contacted, regional registries and hospital patient data will be used to find the patient.

Once the patient has been found or contacted, referral to HUIL will be offered to him. The harm reduction team accompanies the drug user to hospital to be evaluated by a practitioner with expertise in assessment of liver disease severity and HCV treatment. In the first visit to the hospital, a part from the medical history and physical examination, a blood test and a Fibroscan® will be performed. These blood tests will confirm the results from the screening for HCV in Cañada Real.

At this point, all PWID will be offered substitution therapy with methadone and referral to a detoxification center. If the patient accepts, he will then be taken to a detox center to start HCV therapy and where he will stay for an average of six months. If the patient does not accept referral to a detox center, the mobile harm reduction unit will administer therapy (directly observed therapy) to him and will be in charge off his follow up in the shantytown.

Hepatitis C therapy will be prescribed according to European and regional guidelines. Current guidelines recommend treating PWID independently of the liver fibrosis stage. In this project, antiviral therapy will be chosen regarding interactions with other drugs or methadone and a once-daily therapy is preferred in those patients who decline being referred to a detox centre.

After HCV therapy has been completed, all PWID will be periodically screened for hepatitis C (analyzing RNA HCV) to detect infection. Depending on the drug users risk factors, screening for reinfection of HCV will be carried out on a 3 to 6 months schedule.

Infanta Leonor Hospital (HUIL) is the reference specialized health centre for Cañada Real shantytown. All PWID diagnosed of HIV and HCV in this shantytown are referred to the HUIL internal medicine department for evaluation. The hospital is highly coordinated with the harm reduction unit. Nurses or doctors from the harm reduction unit accompany the patients to the specialized clinic.

ETHICAL ISSUES

All patients will sign an informed consent form. Confidentiality will be maintained with regard to personal and genetic data in accordance with the basic ethical principles for research involving biological samples and the provisions of applicable legislation (Organic Law 15/1999 of 13 December on Data Protection, Law 41/2002 on Patient and Healthcare Autonomy and Law 14/1986 on General Health). The ethical research principles set out in the Declaration of Helsinki and the Belmont Report will be adhered to, as will those of the UNESCO Universal Declaration on the Human Genome and Human Rights. The requirements of Spanish legislation on processing on personal data will also be met. The research project has been approved by the Research Committee at HUIL and the Ethics Committee of Hospital General Universitario Gregorio Marañón and ISCIII.

LIMITATIONS OF THE STUDY

The study may be limited by the possibility of not reaching the required number of subjects, although we believe this to be unlikely given the large number of people who visit Cañada Real Galiana. Furthermore, the limit of HCV detection by real-time PCR is approximately 1000 IU/mL, although we believe that with this limit we may detect the vast majority of active infections, since HCV viral load in untreated patients tends to be greater than 1000 IU/mL. Moreover, previous publications show 94% sensitivity and specificity for the Whatman card.

In contrast with the rapid tests, sample processing is centralized, so results are not available immediately. Given that screening is performed in an unfavorable setting and on an outpatient basis, a series of problems could arise, as follows: (1) errors in the processing of samples (eg, insufficient sample volume contamination, loss); (2) difficulties in contacting participants once the results are available; and (3) the assumption that although a significant percentage of consumers will consent to screening, many will refuse referral to a health center for confirmation of diagnosis and treatment.

GENERAL TASKS

1. Administrative tasks: Classification by the Spanish Agency for Medicines and Medical Devices (AEMPS) and presentation to the Clinical Research Ethics Committee (CEIC).
2. Contracting of IT services. Design of online data collection forms.
3. Final design of protocol and informed consent forms.
4. Design of database and adaptation of online data collection forms.
5. Initial meeting of researchers.
6. Six-monthly teleconferences for researchers.
7. Phase 1: Recruitment, collection of informed consent forms, collection of

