2.6 Study Duration

2.7 Statistical Analysis and Sample Size Justification

PHASE I

Once all subjects have been included, the results from the Whatman 903 cards will be compared with those obtained by venipuncture at HUIL. Diagnostic performance will be assessed by calculating the area under the ROC curve (AUROC) for each virus. The Se, Sp, PPV, and NPV for each virus will also be calculated.

PHASE II

Sample size: Assuming that around 10,000 people visit Cañada Real Galiana on different days, a sample size of 930 randomly selected subjects will suffice to estimate, with a 95% confidence interval and a precision of ± 3 percentage points, a

population percentage considered to be around 60%. A replacement rate of 0% has been anticipated.

PHASE III

In order to evaluate the effectiveness of the intervention, the accuracy of HCV tests will be calculated at the population level (AUROC, Se, Sp, PPV, and NPV), as will the percentage of patients arriving at the clinic, the percentage of patients treated, and the percentage of patients cured of hepatitis C. The incidence of HCV reinfection will be assessed using a Kaplan-Meier survival method. In addition, the effectiveness of the intervention for HIV, HBV, and HDV infection will be evaluated.

Statistical Methods

The statistical analysis will be performed using IBM SPSS Statistics for Windows, Version 22.0 (IBM Corp, Armonk, New York, USA) and the R statistical package, version 3.2.2 (GNU General Public License). All tests will be two-tailed, with p-values of <0.05 considered statistically significant.

An assessment will be performed to determine the percentage of patients who are positive at screening, are referred to a health center, have their diagnoses confirmed, and are treated at the end of the study. Factors associated with virus transmission, lack of referral to a health center, and HCV treatment will also be analyzed.

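### The objective asks whether card screening improves detection, referral, treatment and cure, but Phase III gives only single-group percentages, so no gain over the unit's existing pathway can be concluded or credited to the card

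*Combined protocol and SAP*

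**What the plan says.** The question in section 2.1 is comparative. The hypothesis expects the method to "increase the frequency of referral to hospital and administration of appropriate HCV treatment and thus reduce the prevalence of HCV", and the overall objective asks whether it "can improve the localization of HCV-infected patients for subsequent referral to the Hospital, administration of HCV antiviral therapy and cure of hepatitis C". Main objective 3 then attributes the effect on patients' health to the alternative test itself.

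Section 2.3 labels the design "DESIGN OF THE STUDY: Cross-sectional" and describes one screened group. Section 2.7, Phase III, says effectiveness will be judged by test accuracy, "as will the percentage of patients arriving at the clinic, the percentage of patients treated, and the percentage of patients cured of hepatitis C", and by reinfection incidence. The Statistical Methods paragraph adds the percentages screened positive, referred, confirmed and treated, and an analysis of factors associated with non-referral. No control group, baseline rate, benchmark or success threshold is given for any cascade step.

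Section 2.2 describes the unit's existing work in the present tense: "This harm reduction unit identifies drug users at risk, offering them needles, syringes, opioid substitution therapy and screening for HIV and HCV". It goes on: "The harm reduction team accompanies the drug user to hospital and ensures his follow-up and adherence to therapy". Section 2.3, Phase II, offers the card to everyone approached, whether or not their HCV status is already known.

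**The concern.** A percentage of positives who reach the clinic cannot show improvement unless it is set against something. Existing practice at this site is not zero: screening, referral to the same hospital and accompaniment are all described as already running. A linkage figure from the programme therefore mixes what the existing pathway would have delivered with whatever the programme added.

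Two features make the mixing worse. Because known status is no bar to testing, people already diagnosed or under follow-up can count as detected and linked. In addition, the card does not arrive alone: section 2.3, Phase II, brings nurses hired for the purpose and an active search. Even a real gain would belong to that combination.

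At stake is what the final report may claim. A reader could take a good-looking cascade as evidence that the card improved care, although the plan contains nothing that supports the step from description to improvement.

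**Working it through.** **1. What the sample size was built for.** Inputs from section 2.7, Phase II: proportion 0.60, precision ±0.03, 95% confidence, population 10,000, replacement 0%.

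- n0 = 1.96² × 0.6 × 0.4 / 0.03² = 1,024.4
- With finite population correction: 1,024.4 / (1 + 1,023.4/10,000) = 929.3, rounded up to 930.

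The stated 930 reproduces. It is a one-proportion precision calculation, with no second group, effect size or power.

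**2. What the plan can estimate.** If the 60% is read as the positive fraction, positives = 930 × 0.60 = 558. The half-width for a cascade percentage q is 1.96 × √(q(1 − q)/558):

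- q = 0.30 or 0.70: 3.8 points
- q = 0.50: 4.1 points

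Description is therefore reasonably precise. Section 2.7 does not say whether the 60% is antibody or active infection. Fewer positives would widen these figures.

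**3. What it cannot estimate.** Suppose 50% of positives reach the clinic (assumed). The difference from existing practice is 50% minus an unknown rate. If that rate were 30%, 50% or 60% (all assumed), the difference would be +20, 0 or −10 points. Nothing planned distinguishes these cases.

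**4. How much prior status can hide.** Section 2.2 estimates that 40% of infected people in Spain have been diagnosed. The site figure is not given and may differ in either direction; across all possible values, newly identified positives range from 0 to 558. Taking 40% as an illustration:

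- already known: 558 × 0.40 ≈ 223; newly identified: 558 − 223 = 335
- reaching the clinic at 50%: 558 × 0.50 = 279
- if all 223 known cases arrive: 279 − 223 = 56 of 335 new cases, or 17%
- if no known case arrives: 279 of 335, or 83%

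A pooled 50% is thus compatible with linkage of 17% to 83% among newly found infections. Reported separately, a 50% rate would have a half-width of 1.96 × √(0.25/335) = 5.4 points for new cases and 1.96 × √(0.25/223) = 6.6 points for known cases.

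**5. What an optional historical comparison would give.** Assume 30% linkage among n earlier positives and 50% among 558. The half-width of the difference is 1.96 × √(0.25/558 + 0.21/n): 9.9 points (n = 100), 7.6 (n = 200), 6.6 (n = 300). These intervals cover sampling error only. The earlier rate and counts are assumptions, and the documents do not show that such records exist.

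**The case against.** The strongest reply is that this is openly a descriptive implementation study. It is called cross-sectional, is sized for one proportion, and objective 3 itself defines effectiveness as referrals, numbers treated and percentage cured. That is largely right and explains why the remedy is mainly wording. It does not rescue the word 'improve' or the credit given to the test.

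Several stronger readings are tempting, and the documents do not support them.

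- *A reader might infer that nothing is known about participants' starting point.* The Phase II variables in section 2.7 record earlier offers of testing and their results, current HCV monitoring, and contact with health services. What is missing is an analysis that uses them.
- *A reader might infer that no change of any kind can be seen.* Secondary objectives 4 and 6 give prevalence of active infection initially and 24 months after the first intervention. This is uncontrolled, has no stated comparison and does not cover the cascade, but it is a second time point.
- *A reader might treat the detoxification offer and directly observed therapy as new components arriving with the card.* The documents do not say they are new; section 2.2 already describes substitution therapy and adherence support. The bundling argument rests on the dedicated nurses and active search.
- *A reader might take the Phase III statement that "All PWID diagnosed of HIV and HCV in this shantytown are referred to the HUIL internal medicine department for evaluation" as proof of earlier practice.* It stands inside the study's own procedures, so section 2.2 has to carry that point.
- *A reader might think a look back at earlier records would settle the question.* Under current practice (section 2.2) RNA confirmation follows serology at a later visit, so earlier confirmed cases would be selected by who returned. The national hepatitis C plan, in force since April 2015, would confound any before-and-after contrast.

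The venous sample is a comparator for test accuracy only.

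**Conclusion.** The concern holds in a bounded form. As written, the overall objective and main objective 3 cannot be answered by the Phase III output: no improvement over existing practice in detection, referral, treatment or cure can be concluded, and none can be credited to the card alone. The study remains useful as a description, with cascade percentages precise to about 4 points if there are about 558 positives.

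The gap is between the claim and the analysis; the sample-size arithmetic is sound for its own purpose. The conclusion does not depend on the illustrative rates: without a reference value, the sign of the difference is unknown at any observed percentage. The 17% to 83% range does depend on the 60% being the positive fraction, the national 40% applying at the site, and the assumed 50% reaching the clinic.

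**What to change.** **Section 2.1.** Restate the overall objective and objective 3 as describing the care cascade (screened, positive, seen at the hospital, treated, cured) achieved by the programme as a whole, with 95% confidence intervals. Drop 'improve' and the attribution to the test.

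**Section 2.7, Phase III.** Report the cascade separately for:

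1. newly identified infections;
2. infections already known but not in care;
3. infections already known and monitored.

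Fix the definitions before analysis from the prior-test result, HCV-monitoring and health-centre-contact variables. The first two rows make visible what the programme may have added. They are an upper limit, because the unit's ordinary screening might have found some of these people.

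**Cost.** Wording and one stratified table, with no new data collection. The conclusion becomes more modest. Prior status is self-reported, and the listed prior-test item does not separate antibody from RNA results.

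**Optional.** A comparison with the unit's and hospital's records from before the programme, only if usable records exist and access is approved; the documents establish neither. It must be labelled as open to time trends, including the national plan.
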